## 8.7 Multicenter Consideration

Analyses adjusting for analysis center will be conducted. Analysis centers are the same as investigative sites if the number of randomized subjects in a site is equal to or larger than 10. All investigative sites with number of randomized subjects in a site less than 10 will be pooled into an analysis center for analyses.

## 9. Disposition of Subjects

Disposition will be presented in terms of numbers and percentage of subjects by treatment group and for all subjects. Percentages will be calculated using number of randomized subjects as the denominator unless otherwise specified.

The number of subjects screened, screen failed, entered run-in period, and randomized will be presented. Provided that subjects may be rescreened once after initial screen failure, each subject will be reported based on his/her final enrollment status, i.e., screen failure, randomized.

The number and percentages of subjects in each analysis population (ITT, PP, and Safety) will be presented.

The number and percentages of subjects who completed the study or discontinued from the study will be presented. The reasons for study discontinuation to be summarized will include AE, withdrawal of consent, non-compliance, lost to follow-up, disallowed concurrent treatment, pregnancy, lack of efficacy, investigator decision, protocol deviation, death, and other.

The number and percentages of subjects with any protocol deviation, major deviation, minor deviation, or COVID-19 related deviation will be presented.

Subject listings including subject disposition for randomized subjects and screen failed subjects separately, informed consent, violation of inclusion/exclusion criteria, protocol deviations, and analysis populations, will be provided. In addition, details of the study randomization, including randomization date and time, randomized treatment, actual treatment, qualifying eye, and study eye will also be included in a subject listing.

## 10. Demographic, Baseline Characteristics, and Other Pre-treatment Variables

### 10.1 Demographic and Baseline Characteristics

The demographic variables collected in this study include age, sex assigned at birth, childbearing potential for female subjects and method of contraception for female subjects with childbearing potential, race, ethnicity, and iris color. Subjects who record more than one race will be grouped into a single category denoted as Multi-racial. Iris color will be summarized at the subject level for study eye and fellow eye separately. Demographic variables will be summarized using ITT population and Safety population separately.

Age (years) will be summarized, overall and by treatment group, using continuous descriptive statistics. Age will also be categorized as follows: 30 – 45 years, 46 – 60 years, 61 – 75 years, and > 75 years. The number and percentage of subjects will be presented, overall and by treatment group, for age category, sex, race, ethnicity, and iris color of both study eye and fellow eye.

A subject listing that includes all demographic variables will be provided. In addition, subject listings will be provided for the childbearing potential and pregnancy test results, separately, for female randomized subjects.

## **11. Medical History, Prior and Concomitant Medications, and Concomitant Procedures**

### **11.1 Medical History**

Medical history will be obtained at the Screening visit and coded using Medical Dictionary for Regulatory Activities (MedDRA) Version 25.0 and summarized using Safety population.

Ocular medical history and non-ocular medical history will be summarized separately using discrete summary statistics, overall and by treatment group, at the subject level by System Organ Class (SOC) and Preferred Term (PT) using the Safety population. Percentages will be based on the number of subjects in

each treatment group. If a subject reports the same PT multiple times within the same SOC, that PT will only be reported once within that SOC. If a subject reports multiple conditions within the same SOC, that SOC will only be reported once. In the summaries, SOCs and PTs within a SOC are listed in order of descending frequency across all subjects.

Subject listings of medical history will be generated separately for ocular and non-ocular data.

## **11.2 Prior and Concomitant Medications**

Prior and concomitant medications will be coded using the World Health Organization (WHO) Drug Dictionary (B3, March 2022) and summarized to the therapeutic drug class (Anatomical Therapeutic Chemical [ATC] 4 classification) and preferred name. If the ATC 4 classification is not provided, then the next highest classification that is provided in the coding dictionary will be used. The preferred name will be defined as the active ingredient; if the active ingredient is not provided or includes more than two ingredients (e.g., multivitamins), then the drug name will be summarized as the preferred name.

Concomitant medications are defined as those medications listed as having been taken (1) prior to initiation of study intervention administration and continuing for any period of time following the first administration of study intervention or (2) at any time on or after the first administration of study intervention.

Ocular and non-ocular concomitant medications will be summarized separately using the Safety population. Medications will be tabulated by treatment group using frequencies and percentages. Subjects may have more than one medication per ATC. At each level of subject summarization, a subject will be counted once if he/she reports one or more medications. Percentages will be based on the number of subjects in each treatment group. In the summaries, ATC classes and preferred names within an ATC class will be listed in order of descending frequency across all subjects.

A subject listing of prior and concomitant medications will be generated.

## **11.3 Concomitant Procedures**

Concomitant procedures or surgeries performed during the study period will be coded using the Medical Dictionary for Regulatory Activities (MedDRA) Version 25.0 and presented in a subject listing.

# **12. Dosing Compliance and Treatment Exposure**

## **12.1 Dosing Compliance**

At the Screening visit, the morning dose will be administered in clinic by the subject under supervision from site personnel. For the Baseline (Day 1), Day 7, Day 14, Day 28, and Day 90 visits, the “evening” dose will be administered by designated site personnel; all other doses will be administered by the subject. Study intervention compliance will be assessed by site records for these treatments.

The subjects' used and unused study intervention vials will be collected on the Treatment Accountability Log eCRF page from the Baseline (Day 1) visit up to and including the Day 90 (or Early Termination [ET] ) to assess dosing compliance. If the subject's compliance between visits is less than 80% or more than 125% based on the expected number of used and unused vials, then the subject will be deemed non-compliant, and a protocol deviation must be recorded. The study centers will keep an accurate accountability record that specifies the amount of study intervention dispensed to each subject, the amount of study intervention returned to the site, and the dates of each.

Overall study intervention dosing compliance (% compliance) starting from Baseline (Day 1) to Day 90 (or ET) will be assessed by:

$$\text{Compliance (\%)} = \frac{\text{Number of Actual Doses Received}}{\text{Number of Expected Doses}} \times 100$$

The number of actual doses received is calculated as the following:

$$(\text{sum of "Number of Vials Used" recorded on Treatment Accountability Log}) + 1$$

The adjustment of +1 will be applied to subjects who have Day 90 in-office dosing completed after the Treatment Accountability Log for Day 60 kits are recorded.

The number of expected doses is calculated as the following:

$$2 \times (\text{Date of Last Dose} - \text{Date of First Dose}) + 1$$

for all subjects, regardless of study completion status. The adjustment of +1 is because there will be only one "evening" dose on the day of the first dose and two doses are expected for all other days till study exit. The date of last dose is the latest non-missing dosing date collected on the Study Drug Administration eCRF page or the Study Exit eCRF page, and the date of first dose is collected on the Study Drug Administration eCRF page.

Dosing compliance will be summarized numerically using continuous descriptive statistics and categorically (< 80%, >= 80% and <= 125%, and > 125% compliance) using counts and percentages for each treatment group using Safety population. When subjects have abnormal data entries caused by data issues, dosing compliance may not be calculated. Subject listings of study drug dispensation, treatment kit accountability, and in-office study drug instillation will be provided. In addition, a subject listing for run-in administration and dispensation will be provided separately.

## 12.2 Treatment Exposure

Treatment exposure will be defined as the number of days that the subject was exposed to study intervention as calculated using the formula:

$$\text{Treatment Exposure Duration (days)} = \text{Date of Last Dose} - \text{Date of First Dose} + 1.$$

Treatment exposure duration in days for each subject will be summarized with continuous descriptive statistics for each treatment group using the Safety population. The date of last dose is the latest non-missing dosing date collected on the Study Drug Administration eCRF page or Study Exit eCRF page, and the date of first dose is collected on the Study Drug Administration eCRF page.

### **13. Efficacy Analyses**

Primary, secondary, [REDACTED] assessments are described in [Section 13.1](#), [Section 13.2](#), [REDACTED] [REDACTED]. Subject listings will be produced for each efficacy assessment. In addition, the primary, secondary, [REDACTED] analyses are specified in [Section 13.4](#), [Section 13.5](#), [REDACTED] [REDACTED] [REDACTED].

#### **13.1 Primary Efficacy Assessments**

##### **13.1.1 UNANESTHETIZED SCHIRMER TEST**

Schirmer's test determines whether the eye produces enough tears to keep it moist. Two unanesthetized Schirmer tests (one pre-drop test and one post-drop test) for each eye will be performed at Baseline (Day 1), and Days 7, 14, 28, and 90. Greater Schirmer scores indicate greater amount of tears produced (or better results).

#### **13.2 Secondary Efficacy Assessments**

##### **13.2.1 SYMPTOM ASSESSMENT IN DRY EYE QUESTIONNAIRE**

The SANDE questionnaire is comprised of 2 unique VASs to assess the frequency and severity of DED symptoms. Subjects will be asked to complete the SANDE to rate both the frequency and severity of DED symptoms for both eyes together. Each of the two questions will be accompanied by a VAS. The assessment line length of the scale will be 100 mm and will be similar to the following depiction (Figure 3). Higher scores indicate greater frequency or severity of symptoms of dryness and/or irritation. In addition, a global SANDE score is also collected in the eCRF, which is calculated by multiplying the frequency score by the severity score and obtaining the square root rounded to the nearest whole number.

The SANDE will be administered at Screening, Baseline (Day 1), and Days 7, 14, 28, and 90. The frequency, severity and global SANDE score will be summarized.

### Figure 3. SANDE Questionnaire Example

**PLEASE COMPLETE THE FOLLOWING QUESTIONS REGARDING THE FREQUENCY AND SEVERITY OF YOUR DRY EYE SYMPTOMS:**

### 1. Frequency of symptoms:

Place a single vertical mark on the horizontal line to indicate how often, on average, your eyes feel dry and/or irritated.

## 2. Severity of symptoms:

Place a single vertical mark on the horizontal line to indicate how severe, on average, you feel your symptoms of dryness and/or irritation.

### 13.2.2 SYMPTOM QUESTIONNAIRE

Subjects will be asked to rate each of the following DED symptoms (OU), over the last 24 hours, each on a separate VAS: ocular discomfort (ODS), eye dryness (EDS), [REDACTED] For each VAS, subjects will be asked to place a vertical mark on the horizontal line to indicate the level of each symptom, with 0 corresponding to "No Symptom" and 100 corresponding to "Maximal Symptom". The assessment line length of the scale will be 100 mm and will be similar to the following depiction (Figure 4). The questionnaire will be administered at Screening, Baseline (Day 1), and Days 7, 14, 28, and 90. The ODS, EDS, [REDACTED] scores will be summarized separately.

[figure not shown]
**Figure 4. Symptom Questionnaire Example**

## Ocular Discomfort: Visual Analog Scale

## Eye Dryness: Visual Analog Scale

[figure not shown]

### 13.4 Primary Efficacy Analysis

[figure not shown]
The primary comparison in this trial will be between AR-15512 (0.003%) and vehicle in the ITT population using Estimand 1 ([Section 2.3.1](#)).

[figure not shown]
The frequency and percentage of subjects with  $\geq 10$  mm increase (Post-drop Measure on Day 14 – Pre-drop Measure at Baseline [Day 1]) in unanesthetized Schirmer score will be summarized by treatment group. Testing of the difference in proportion of subjects with  $\geq 10$  mm increase in unanesthetized Schirmer score on Day 14 will use Pearson's Chi-square test. The differences in proportions along with corresponding two-sided 95% CIs based on asymptotic normal distribution and p-values from Pearson's Chi-square test will be presented.

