#### 2.1.1 PRIMARY ENDPOINT

- Proportion of subjects with  $\geq 10$  mm increase (post-drop on Day 14 vs pre-drop at Baseline) in unanesthetized Schirmer score on Day 14

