## 2.3 Estimands

### 2.3.1 ESTIMAND 1 (PRIMARY ESTIMAND)

The primary comparison will be based on the ITT population targeting the treatment effect attributable to the randomly assigned treatment, regardless of compliance to study treatment and assuming subjects who discontinued due to lack of efficacy, AEs, or disallowed concurrent treatments follow the behavior of subjects in the reference arm for the duration of the study and subjects who discontinued for other reasons (outside of lack of efficacy, AEs or use of disallowed treatment) would follow the behavior of subjects who are still in the study under same randomly assigned treatment.

- Population: subjects in the ITT population with DED defined through enrollment criteria
- Endpoint:
  - Proportion of subjects with  $\geq 10$  mm increase in unanesthetized Schirmer score on Day 14
- Intercurrent event:
  - Non-optimal treatment compliance is ignored. [treatment policy strategy]
  - Withdrawal due to lack of efficacy, AEs, or disallowed concurrent treatment - multiple imputations using vehicle treatment group regardless of randomized treatment group is used to impute missing data. [hypothetical strategy, missing not at random]
  - Withdrawal due to reasons other than lack of efficacy, AEs, or disallowed concurrent treatment - multiple imputations using randomized treatment is used to impute missing data. [hypothetical strategy, missing at random]

- Population-level summary:
  - Difference in the proportion of subjects with  $\geq 10$  mm increase in unanesthetized Schirmer score on Day 14 between AR-15512 (0.003%) and vehicle

[figure not shown]

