#### **4. Study Treatments**

##### **4.1 Method of Assigning Subjects to Treatment Groups**

All subjects will be centrally assigned to randomized study intervention using interactive response technology (IRT). Before the study is initiated, the log-in information and directions for the IRT will be provided to qualified personnel at each site.

All qualified subjects will be assigned to receive AR-15512 vehicle BID to both eyes for approximately 14 days during the vehicle run-in period. Following the run-in period, all subjects who requalify at Baseline (Day 1) will be randomized in a 1:1 ratio, within each site, to receive 0.003% AR-15512 or AR-15512 vehicle. The IRT will provide the site with the specific kit number(s) for each randomized subject at the time of randomization. Sites will dispense the study intervention according to the IRT instructions and the Schedule of Visits and Assessments as in Table 1.

Individuals who do not meet the criteria for participation in this study (screen failures) may be rescreened for eligibility up to one time if there is reasonable possibility, in the Investigator's opinion, that the patient might meet the eligibility criteria. When a subject is rescreened, a new subject ID will be assigned, and the previous subject id will be recorded in the Informed Consent CRF form.

The subject ID will be in the format of xxx-xxx, with the first 3 characters being the site number and the last 3 characters sequentially numbered starting from 001 within the site, which will be used to identify subjects in all datasets and listings for this study.

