## **5. Sample Size and Power Considerations**

Two hundred two (202) ITT population subjects (study eyes) per treatment group yields 99% power to conclude superiority of 0.003% AR-15512 over vehicle in the proportion of subjects with  $\geq 10$  mm increase in unanesthetized Schirmer score on Day 14, assuming a true difference of proportions (AR-15512 vs vehicle) of 80% vs 30% and a two-sided alpha=0.05.

Additionally, 202 ITT population subjects (study eyes) per treatment group yields 99% power to conclude superiority of 0.003% AR-15512 over vehicle in the mean change from baseline in SANDE score on Day 28 assuming a true difference (AR-15512 minus vehicle) of -8.3, a common standard deviation (SD) of 17.72, and a two-sided alpha=0.05.

Accounting for subject discontinuations, approximately 460 total subjects (230 per treatment arm) will be randomized assuming a dropout rate of 10%.

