#### 8.4 Definition of Baseline

Baseline is defined as the last non-missing measure prior to the initiation of randomized study intervention.

- The efficacy endpoint baseline will be the Baseline (Day 1) measurement. Screening visit and unscheduled visit measurements if any prior to the initiation of randomized study intervention **will not be considered** for baseline even when Baseline (Day 1) measurement is missing.
- For unanesthetized Schirmer test measures taken at both pre-drop and post-drop, the pre-drop measure at Baseline (Day 1) will be the baseline for primary and secondary analyses as specified

in Sections 2.1.1 and 2.1.2, [REDACTED]  
[REDACTED]

- The safety endpoint baseline will be the Baseline (Day 1) measurement. When Baseline (Day 1) measurement is missing, the last non-missing measurement from Screening visit and unscheduled visit measurements prior to the initiation of randomized study intervention **will be considered** for baseline.

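### The primary responder test ignores the within-site randomisation and baseline Schirmer: valid, but mildly conservative for the trial's own sites if sites differ, and slightly less precise if baseline is prognostic

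*SAP*

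**What the plan says.** The primary endpoint (SAP 2.1.1) is a responder status, a 10 mm or greater "increase (post-drop on Day 14 vs pre-drop at Baseline) in unanesthetized Schirmer score on Day 14". SAP 13.4 says that the comparison of proportions in "unanesthetized Schirmer score on Day 14 will use Pearson's Chi-square test", and that "two-sided 95% CIs based on asymptotic normal distribution and p-values from Pearson's Chi-square test will be presented". The readable text has no term for site or baseline. The Protocol synopsis likewise names only difference-of-proportions tests for dichotomous endpoints.

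Elsewhere the SAP provides what an adjusted analysis would need:

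- **Allocation (SAP 4.1).** Subjects "will be randomized in a 1:1 ratio, within each site, to receive 0.003% AR-15512 or AR-15512 vehicle", so site is a stratification factor.
- **Centers (SAP 8.7).** Center-adjusted analyses are announced without naming endpoints, and small sites are handled: "All investigative sites with number of randomized subjects in a site less than 10 will be pooled into an analysis center for analyses".
- **Baseline (SAP 8.4).** For the Schirmer test, "the pre-drop measure at Baseline (Day 1) will be the baseline for primary and secondary analyses".
- **Secondary endpoints (SAP 13.5).** Changes from baseline, including the continuous Day 14 Schirmer change, are analysed by ANCOVA with baseline value, treatment and analysis center.

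The same Day 14 measurement is therefore adjusted as a secondary endpoint and unadjusted as the primary one.

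**The concern.** There are two separate costs, and they differ in kind.

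1. **Site.** Randomising within site already balances the arms across sites, so between-site variation drops out of the real sampling error of the difference. The crude SE still counts it. If sites differ, the test rejects less often than 5% under the null, and the interval is wider than it needs to be for the effect at these sites. Adjusting for site corrects the reported SE. It does not make the estimate itself more precise.
2. **Baseline.** If pre-drop Schirmer predicts response, adjusting for it gives a real but modest gain. Subtracting baseline inside the endpoint is not covariate adjustment, and the SAP itself does both in the ANCOVA.

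At stake are the reported SE, interval and p-value of the primary result, not the validity of the test.

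**Working it through.** **Inputs from the documents.** 202 per arm for power and 460 randomised (230 per arm), "assuming a true difference of proportions (AR-15512 vs vehicle) of 80% vs 30% and a two-sided alpha=0.05" (SAP 5); about 20 sites (SAP 3.1). **Assumptions**, because the documents do not give them: site SD of 0, 0.5 or 1.0 and baseline effect of 0, 0.5 or 1.0 per SD, both on the log-odds scale; permuted blocks of 4.

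**1. The plan's power figure.** z = [0.50 − 1.96·√(2·0.55·0.45/202)] / √((0.16 + 0.21)/202) = (0.50 − 0.0970)/0.0428 = 9.4. Power exceeds 99.99%, so the stated 99% is met; 32 per arm would give 99%.

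**2. Site, under the null (30% vs 30%).** The crude SE is √(2·0.21/230) = 0.0427. With stratified allocation the true SD is that value times √(1 − Var(p_s)/0.21), where p_s is the site response rate. Integrating a normal site effect gives Var(p_s) = 0.0102 at site SD 0.5 and 0.0330 at 1.0. The effective critical value is 1.96 divided by the multiplier.

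| Site SD | Multiplier | Critical value | Null rejection, formula | Null rejection, simulated |
|---|---|---|---|---|
| 0 | 1 | 1.96 | 5.0% | 4.8-5.2% |
| 0.5 | 0.976 | 2.01 | 4.5% | 4.4-4.9% |
| 1.0 | 0.918 | 2.14 | 3.3% | 3.1-3.9% |

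The simulations used 20 sites of 23 or 24, or of 6-40 with sites under 10 pooled, and up to 12,000 trials per scenario. The Cochran-Mantel-Haenszel (CMH) test by site or center rejected in 4.7-5.3%. The empirical SD at site SD 1.0 was 0.0390 both crude and adjusted, which confirms that site adjustment repairs the SE and adds no precision.

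**3. Site, at 80% vs 30%, the trial's own sites.** The crude SE is √(0.37/230) = 0.0401, a half-width of 7.9 points. Removing between-site variance (0.0330 on vehicle and 0.0214 on active at site SD 1.0) gives √((0.37 − 0.0544)/230) = 0.0370, or 7.3 points. At site SD 0.5 it is 7.7 points.

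**4. The same effect, a wider population of sites.** A constant log-odds effect gives risk differences that vary by site, with variance 0.0090 at site SD 1.0. The sampling SD across redrawn sites is √(0.0370² + 0.0090/20) = 0.0427, now above the crude SE of 0.0401. Coverage is 93.4% crude (1.96·0.0401/0.0427 = 1.84) and 91.1% site-adjusted (1.96·0.0370/0.0427 = 1.70). A simulation gave 93.5% and 91.1%.

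**5. Baseline.** Adjusting for baseline in simulation cut the empirical SD by 1.4-2.5% at 0.5 per SD and 5.0-7.6% at 1.0. For example, with baseline 1.0 alone under the null it fell from 0.0425 to 0.0393. With neither effect present, the SE was 0.2% larger. The strength cannot be read off the endpoint's arithmetic. With pre/post correlation 0.3-0.9, the implied log-odds per SD run from −1.3 to −0.4 if the two SDs are equal, and from −0.4 to +1.6 if the post-drop SD is twice the pre-drop SD.

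**6. Multiple imputation.** With 10% missing, 30 imputations and an assumed by-arm imputation model, null rejection was 3.0-3.8% for the chi-square and 3.8-4.6% for the model adjusted for baseline and center. Neither is inflated, and part of the conservatism comes from the imputation itself.

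**The case against.** The strongest reply is that nothing here is wrong. The chi-square is valid, follows the Protocol, matches the sample-size basis and targets the estimand's summary, the difference in the proportion with a 10 mm or greater increase in "unanesthetized Schirmer score on Day 14 between AR-15512 (0.003%) and vehicle". At the planned effect every method rejected in 100% of simulated trials. At moderate assumptions the half-width moves by about 0.2 points on a 50-point difference, and larger shifts need strengths that no document supports. All of that stands, and it sets the priority.

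Two further objections also stand. First, a reader might infer that the crude interval is too wide whenever sites differ. It is not: for a wider population of sites and a large effect, both intervals under-cover, and the adjusted one does so more (step 4). Second, a logistic model with about 21 parameters is heavier than needed. In simulation it rejected 5.3-6.0% under the null unless its variance was corrected.

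A reader might also infer that SAP 13.4 contradicts SAP 8.7, or that no adjusted analysis of the primary endpoint exists. The documents support neither. Section 8.7 names no endpoints, and 13.4 runs from page 38 to 43 in the contents list with much of it unreadable, so a center-adjusted analysis may already be there.

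What survives is narrow: the readable primary test disregards the randomisation strata, for no stated reason, when the center definition is already written.

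**Conclusion.** The point holds as an inexpensive improvement, not as the repair of an error. Type I error is not inflated, and the planned conclusion is not at risk. Under the null, or for the trial's own sites, the primary analysis is conservative if sites differ: slightly at an assumed site SD of 0.5, more noticeably at 1.0. The unused gain from baseline is small and may be zero, since the association could be of either sign.

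Every size rests on assumed prognostic strengths. The interval widths and coverages use complete data, whereas the planned analysis pools over imputations whose model is not visible. The direction of the site effect is secure within the stated condition; its size in this trial is unknown. Priority is low.

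**What to change.** Before unmasking, amend SAP 13.4 as follows:

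- **Primary.** Use a CMH test stratified by analysis center, with the SAP 8.7 pooling, and a Mantel-Haenszel risk difference with its 95% interval. Run both on each imputed dataset and pool. State the variance estimator and the pooling rule for each.
- **Sensitivity.** Keep the unadjusted Pearson chi-square and its interval.
- **Optional.** Prespecify a standardised risk difference from a logistic model with treatment, baseline pre-drop Schirmer and analysis center, as supportive or as primary if the sponsor prefers. Use a robust SE with its variance multiplied by n/(n − p), for example 460/439 with 21 parameters; this brought simulated null rejection to 4.8-5.5%. Add a non-convergence rule, such as falling back to the center-stratified analysis.
- **Binary Schirmer secondaries (Days 1 and 90).** Use the same approach unless redacted text already specifies a method.

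If redacted parts of 13.4 already hold a center-adjusted analysis of this endpoint, promote that one instead.

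The cost is SAP wording and minor programming, with no new data or subjects. The Mantel-Haenszel difference weights centers slightly differently from the crude difference and uses no baseline. Its interval describes the trial's own sites, and the SAP should say so.
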